12. Pregnant or breast-feeding female patient (a female patient of childbearing potential or with amenorrhea for less than 12 months must have a negative urine pregnancy test within 1 day prior to trial MRI and must be using highly effective birth controlled method* until the last trial visit).
13. Patient with known contra-indication(s) to the use or with known sensitivity to one of the products under investigation or to other GBCAs (such as hypersensitivity, post contrast acute kidney injury).

** Highly effective birth controlled method includes: abstinence (defined as refraining from heterosexual intercourse during the entire trial participation), female sterilization (sterilization methods include hysterectomy, bilateral salpingectomy and bilateral oophorectomy), combined (estrogen and progestogen containing) hormonal contraception associated with inhibition of ovulation (oral, intravaginal, transdermal), progestogen-only hormonal contraception associated with inhibition of ovulation (oral, injectable, implantable), intrauterine device (IUD), intrauterine hormone-releasing system (IUS), bilateral tubal occlusion, vasectomized partner (vasectomized partner is a highly effective birth control method provided that partner is the sole sexual partner of the female patient and that the vasectomized partner has received medical assessment of the surgical success.). Periodic abstinence (calendar, symptothermal, post-ovulation methods), withdrawal (coitus interruptus), spermicides only, and lactational amenorrhoea method (LAM) are not acceptable methods of contraception. Female condom and male condom should not be used together.*

The diagnosis obtained from previous (qualifying) imaging examinations will be considered as medical history to assess inclusion criteria. All the trial efficacy analyses will be only based on the images obtained through the trial MRI.

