6 CONCOMITANT MEDICATIONS / PROCEDURES

6.1 Concomitant Medications

Any medication, including contraception, homeopathic products, pre-medication, over-the-counter medications, as well as prescription drugs, on-going at the time of patient's informed consent signed or administered during the trial will be recorded in the patient's medical file and in the patient's clinical electronic Case Report Form (eCRF). The following information must be provided:

- Drug (brand name or generic name)
- Route of administration
- Purpose (medical history/trial disease/AE/pre-medication/contraception/prophylaxis)
- Indication
- Start/end period: before first administration, between first and second administration, after second (last) administration, ongoing at the end of the trial.

6.1.1 *Concomitant Medications of Special Attention*

Currently, no treatment has been identified that is capable of preventing an allergic reaction with any GBCA. Thus, no pre-treatment of any nature will be recommended before contrast-enhanced MRI. Nevertheless, if the investigator decides to premedicate a patient, the treatment must be documented in the medical file and then in the clinical eCRF.

In general, there are no specific recommendations regarding GBCAs, and therefore, no specific hydration procedure is defined in this protocol. Nonetheless, whenever possible, the patient should be encouraged to drink water and other non-alcoholic fluids liberally before and after the injection.

According to current knowledge, there is no other concomitant treatment of special attention in that trial. However warnings and precautions for use of the concomitant treatments taken by the patient should be considered.

In addition, no significant change should occur in any treatment or medical procedure (e.g. chemotherapy, radiotherapy, biopsy or surgery etc...) which may impact the appearance of lesion of the imaged body region between the 2 MRI examinations. However, patients under corticosteroids and/or maintenance chemotherapy with a stable dose at the time of screening visit and throughout the trial can be included.

6.1.2 *Prohibited Concomitant Medications*

Any contrast agent (MRI or CT) within 3 days prior to trial products administration and during the course of the trial or within 24 hours after the second trial product administration are prohibited.

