- Blood sample collection for serum creatinine dosage and verification that the local eGFR value is ≥ 30 mL/min/1.73 m²; The same local methods of serum creatinine dosage and eGFR calculation should be used throughout the trial for a same patient;
- Blood samples will be collected according to central laboratory manual;
- Assessment of local serum creatinine results as per ESUR guidelines (see [section 7.2.11](#))
- Assessment of AEs will be documented;

- IWRS connection will be done to obtain the IMP box number, to calculate the volume of IMP to be administered based on the body weight and to record the date of the visit;

Unenhanced and contrast-enhanced MRI examinations:

- Unenhanced and contrast-enhanced MRI will be performed according to the required sequences specified in [Section 8.2.2](#).

The appropriate dose/volume of gadopiclenol and gadobutrol will be administered by IV as a bolus using preferably a power injector in a peripheral vein of the antecubital region (recommended). IMP injection will be followed by a 0.9% saline flush injection.

The following information will be documented in the source document and reported on clinical eCRF pages: contrast agent injection date and time, location of injection site, actual volume administered (documentation of difference with theoretical volume), actual injection rate, overdose (if any), number of vials dispensed, number of IMP injected, injection method (power injector or manual), injection of saline flush (yes/no).

The start time of contrast injection will be recorded.

Procedures to be followed after MRI examination:

The patient will stay at the trial site for 60 ± 15 min after the MRI examination is completed and the following procedures will be performed:

- Use/change of concomitant treatments during the visit will be documented;
- Vital signs (systolic and diastolic BP and PR) will be obtained 60 minutes ± 15 minutes after the injection of contrast agent.
- Injection-site tolerance (pain, eruption, extravasation, inflammation, or other) will be assessed during the injection and 60 minutes ± 15 minutes after the injection of contrast agent; In case of pain, the patient will have to complete a Numeric Pain intensity scale to indicate the pain intensity. Any sign of local intolerance will be reported as AE in the corresponding clinical eCRF page.
- Assessment of AEs will be documented;
- Evaluation of the potential impact of IMP-enhanced MRI on patient treatment plan;

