#### Protocol deviations

As per International Conference on Harmonization (ICH) E3 guideline, a protocol deviation is any change, divergence or departure from the trial design or procedures defined in the protocol, with or without impact to the patient safety or the efficacy assessments.

Protocol deviations will be gathered from monitoring files, clinical database and external vendors of off-site data (imaging data, laboratory data, IWRS).

If the reason of deviations is related to the COVID pandemic then it will be indicated in the Statistical Review Meeting Minutes and the corresponding deviation presented apart

Protocol deviations will be split in major and non major deviations. A major deviation is defined as a deviation having an impact on the primary criteria 1 or primary criteria 2. The initial categorization is proposed in this document, the final categorization will be performed before breaking the blind. The decision will be duly described in the meeting minutes.

The deviations are listed in the table below:

Category	Description	Source	Status
Inclusion criteria not met/ Non inclusion criteria met	Inclusion criteria n°6 not met: Patient not having read the information or not having provided his/her consent to participate in writing by dating and signing the informed consent prior to any trial related procedure being conducted	Clinical data base	Major
	Non inclusion criteria n°1 met: Patients with known	Clinical data base	Major

Category	Description	Source	Status
	or suspected lesion(s) referred for contrast-enhanced MRI of CNS or of heart or for MR Angiography.		
	Non inclusion criteria n°6 met: Patient having received any contrast agent (MRI or CT) within 3 days prior to first trial product administration, or scheduled to receive any contrast agent during the course of the trial or within 24 hours after the second trial product administration	Clinical data base	Non major
	At least one inclusion criteria except n°6 not met	Clinical data base	Non major
	At least one non -inclusion criteria except n°1 and n°6 met	Clinical data base	Non major
	eGFR at visit 2 or visit 4 below 30 mL/min/1.73m  and contrast agent administration performed	Clinical data base	Non major
	eGFR not measured within one day before contrast agent administration	Clinical data base	Non major
	eGFR measurement at visit 2 or visit 4 is missing	Clinical data base	Non major

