	No pregnancy test done within 1 day before contrast agent administration for female of childbearing potential	Clinical data base	Non major
	Result of pregnancy test positive and contrast agent administration performed	Clinical data base	Non major
Trial disease	Procedure used for detecting the trial disease is not provided	Clinical data base	Non major
	Procedure used for detecting the trial disease is not adequate	Clinical data base	Non major
	Procedure used for detecting the trial disease is not performed within 12 months prior to ICF signature	Clinical data base	Non major
Imaging	Not matching lesion: among patients with gadopiclenol MRI examination available, those with no matching enhancing lesions on paired and pre contrast images for all off-site readers	Imaging data base	Major criteria1
	Not matching lesion: among patients with both MRI examinations available, those with no matching enhancing lesions at both examination for all off-site readers	Imaging data base	Major criteria2
	Imaging protocol not respected with major impact on co-primary criteria for gadopiclenol administration	Monitoring	Major
	Imaging protocol not respected with major impact on co-primary criteria for gadobutrol administration	Monitoring	Major criteria2
	Imaging protocol not respected with non-major impact on primary criterion	Monitoring	Non major
	Deviation to blind charter in regards to data correction	Monitoring	Non major
Unblinding	Blind not maintained on site	Monitoring	Non major

CONFIDENTIAL	STATISTICAL ANALYSIS PLAN PHASE III TRIAL GDX-44-011 VERSION NO. 2.0 DATED 25 JANUARY 2021	████████
		Page 23 / 57

Category	Description	Source	Status
	Blind not maintained at central reading level	Monitoring	Major
Forbidden concomitant medication	Concomitant medication or medical procedure taken between the two MRI significantly impacting lesion size and its enhancement pattern	Clinical data base	Major criteria2
	Patient having received any MRI contrast agent from 3 days prior to first trial product administration, until 24 hours after the second trial product administration	Clinical data base	Major
	Patient having received any CT contrast agent from 3 days prior to first trial product administration, until 24 hours after the second trial product administration	Clinical data base	Non major

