Non respect of study's schedule and procedures	MRI examination with gadopiclenol not performed	Clinical data base	Major
	MRI examination with gadobutrol not performed	Clinical data base	Major criteria2
	Time between the two MRI procedures is strictly greater than 14 days and less or equal to 21 days	Clinical data base	Non major
	Time between the two MRI procedures is strictly greater than 28 days	Clinical data base	Major criteria2
	Two different MRI system manufacturer used for both assessments of the same patient	Clinical data base	Non major
	Two different magnetic field strength used for both assessments	Clinical data base	Major criteria2
	MRI machine used not qualified	Monitoring	Non major
	Body region is different between the two MRs	Clinical data base	Non major
	US patients with an indication other than Breast MRI	Clinical data base	Non major
	Physical examination not performed	Clinical data base	Non major
	eGFR method is not the same throughout the trial	Clinical data base	Non major
	eGFR method is not accurate	Clinical data base	Non major
	Time between screening visit and first contrast agent administration is strictly greater than 7 days	Clinical data base	Non major
	Blood sample for central laboratory assessment is not drawn in the time window allowed by protocol	Clinical data base	Non major
	Vital sign is not measured in the time window allowed by protocol	Clinical data base	Non major
	Tolerance at injection site is not measured in the time window allowed by protocol	Clinical data base	Non major
	Last contact is not between 7 and 14 days after the last injection of IMP for patients recruited in France	Clinical data base	Non major
	Deviation in IWRS Process	Monitoring	Non major
	Clinical protocol procedure not respected	Monitoring	Non major
GCP deviation	Deviations related to ICF signature process	Monitoring	Non major
	Source document management not appropriate	Monitoring	Non major

Patients presenting at least one protocol deviation with a status "**Major**" will be excluded from the PPS1 and PPS2.

Patients presenting at least one protocol deviation with a status "**Major criteria1**" will be excluded from the PPS1

Patients presenting at least one protocol deviation with a status "**Major criteria2**" will be excluded from the PPS2

Frequency and percentages of patients with protocol deviations will be presented breaking down by status (major/non major).

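### Outside MRI contrast given too late to affect the scored images still counts as a Major deviation and removes patients from the per-protocol sets

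*SAP*

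**What the plan says.** The deviation table in SAP 5.2, under forbidden concomitant medication, lists "Patient having received any MRI contrast agent from 3 days prior to first trial product administration, until 24 hours after the second trial product administration" with the status *Major*. The next row applies the same window to CT contrast and is *Non major*.

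Below the table, the SAP states that a patient with at least one *Major* deviation "will be excluded from the PPS1 and PPS2". A deviation marked *Major criteria2* removes the patient from PPS2 only. Above the table stands the governing definition: "A major deviation is defined as a deviation having an impact on the primary criteria 1 or primary criteria 2". The statuses are a proposal at this stage, since "the final categorization will be performed before breaking the blind".

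The window follows the conduct rule in Protocol 6.1.2, under which contrast agents "during the course of the trial or within 24 hours after the second trial product administration are prohibited", as they are in the 3 days before trial product.

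On what is scored, Protocol 4.2 says: "All the trial efficacy analyses will be only based on the images obtained through the trial MRI". On timing at V4, Protocol 8.1.4 says: "The patient will stay at the trial site for 60 ± 15 min after the MRI examination is completed".

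PPS2 is the primary set for objective 2, and FAS2 repeats that analysis. FAS1 is the primary set for objective 1, and PPS1 repeats that analysis (SAP 3.9, 5.6.1 and 5.6.2).

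**The concern.** The row turns a rule about conduct into a rule about analysis sets without asking whether the exposure came before the images it is supposed to have spoiled. A per-protocol exclusion is meant to remove data that the deviation could have distorted. If the exposure came after the relevant images were acquired, the exclusion removes valid data and protects nothing.

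The consequence is greatest for objective 2, because PPS2 decides the non-inferiority claim. A patient with two complete and uncontaminated examinations would be deleted from that analysis. For objective 1 the loss falls on PPS1, which only supports the FAS1 result.

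The table elsewhere makes the distinction that is missing here. Gadobutrol extravasation, a gadobutrol volume error above 20%, a freezing risk for gadobutrol, and an imaging-protocol failure at the gadobutrol examination are all *Major criteria2*. So is treatment between the two MRIs that significantly affects the lesion.

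**Working it through.** **Step 1: which exposures can reach which criterion.** Criteria 1 uses the Pre and Paired images of the gadopiclenol examination only. Criteria 2 uses the Paired images of both examinations (SAP 2.2.1). Protocol 6.1 records each medication as given before the first administration, between the two, or after the second. Crossing those periods with the randomised order gives:

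| Outside MRI contrast only | Order | Can it affect criteria 1? | Can it affect criteria 2? | SAP status | Status by the SAP's definition |
|---|---|---|---|---|---|
| Within 3 days before V2 | gadopiclenol first | possible | possible | Major | Major |
| Within 3 days before V2 | gadobutrol first | possible (see objection) | possible | Major | Major |
| Between V2 and V4 | gadopiclenol first | no, images already acquired | possible | Major | **Major criteria2** |
| Between V2 and V4 | gadobutrol first | possible | possible | Major | Major |
| After the V4 examination, up to 24 h | either | no | no | Major | **Non major** |

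The two rows in bold are the conflict. In the last row every scored image exists before the exposure, because the V4 scan is finished within the visit and only trial images count for efficacy. The few minutes between the second injection and the end of scanning are not part of that row.

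**Step 2: reproduce the plan's sample size for objective 2.** Inputs from SAP 3.3: true difference 0, margin 0.35, SD of the difference 1.75, two-sided 95% confidence interval (one-sided 0.025), 80% power, 200 evaluable patients.

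- Normal approximation: n = (1.75 × (1.960 + 0.842) / 0.35)² = (5 × 2.802)² ≈ 196.3, so 197.
- Paired t-test with the noncentral t distribution, noncentrality (0.35 / 1.75) × √n: n = 199. At n = 200 the noncentrality is 0.2 × 14.142 = 2.828 and power is 80.4%.

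The plan's 200 is reproduced.

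**Step 3: effect of losing patients from PPS2.** The documents give no frequency for this deviation. Assume that PPS2 would otherwise hold 200 patients:

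| Patients lost | n | Power, objective 2 |
|---|---|---|
| 0 | 200 | 80.4% |
| 2 | 198 | 80.0% |
| 5 | 195 | 79.4% |
| 10 | 190 | 78.3% |
| 20 | 180 | 76.1% |

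Losing 2 patients raises the standard error by a factor of √(200/198) = 1.005.

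**Step 4: the PPS1 repeat of objective 1.** With a difference of 0.35 and an SD of 1.5, the same method gives n = 195 for 90% power (200 stated). Power is 90.7% at 200 and 90.4% at 198.

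**The case against.** The strongest reply is that the table is expressly provisional. A blinded review sets the final statuses under a definition that requires impact on a primary criterion, so a post-V4 exposure could be downgraded there. That is true and makes the correction easy. It does not remove the rule as written, and a stated rule is better than case-by-case decisions at a meeting.

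A second reply is that little depends on it. FAS1 is primary for objective 1, FAS2 repeats objective 2 without this exclusion, and few patients are likely to be affected. All of this stands and limits the severity.

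Three stronger readings are tempting, but the documents do not support them.

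- *Pre-V2 contrast in a gadobutrol-first patient cannot matter for criteria 1.* V4 may follow V2 by only 2 days. Contrast given 1 day before V2 would then fall 1 + 2 = 3 days before the gadopiclenol injection, inside the protocol's own restriction. No general downgrade of that case is justified.
- *Set membership is ambiguous, because "Non inclusion criteria n°6 met: Patient having received any contrast agent (MRI or CT) within 3 days prior to first trial product administration" is listed as Non major.* That row is an eligibility row and pools MRI with CT contrast. Since any single *Major* row excludes, aligning the two rows would change no patient's set.
- *The exclusion is linked to outcome and biases non-inferiority.* An early repeat scan after a poor trial image is conceivable. But such contrast is prohibited, the exclusion removes both of a patient's examinations, and order is randomised 1:1. Bias would require post-V4 imaging to depend on the agent, and nothing in the documents shows that.

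**Conclusion.** The row is wrong as written in two parts of its window. Contrast given after the V4 examination cannot meet the SAP's definition of a major deviation for either criterion. Contrast given only between the two administrations in a gadopiclenol-first patient cannot meet it for criteria 1.

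Severity is minor. The first part touches the primary non-inferiority set; the second touches only a supportive set. On the assumed loss of 2 patients from 200, objective 2 power falls by 0.4 percentage points; a loss of 10 would cost 2.1 points. These figures use the plan's SD of 1.75 and illustrate size only, since no count is given. The reason to act is consistency with the SAP's own definition, not power. The planned sample size is unaffected, and neither primary conclusion is shown to be at risk.

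**What to change.** Before unblinding, replace the single MRI-contrast row with three:

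- Outside MRI contrast only after the second administration, once the V4 examination is complete: *Non major*.
- Outside MRI contrast only between the two administrations, in a patient given gadopiclenol first: *Major criteria2*.
- Any other outside MRI contrast in the window, including exposure in more than one period or in a period that cannot be established: *Major*, as now.

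The period field in Protocol 6.1 and the randomised order are sufficient. A clock time is not needed, which matters because SAP 3.5.4 says that none is collected for procedures. The second row depends on the order of agents, so it should be fixed as a rule under the blind and applied by program once the order is released. The existing rows that are specific to gadobutrol also depend on which agent was given. Patients who received the wrong agent are already *Major* under another row, so randomised and actual order agree wherever the new row decides membership.

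The cost is a short SAP revision and a few lines of derivation. Nothing changes for patients or sites, and the protocol's prohibition of outside contrast stays as it is.

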#### 5.4. Demographic and Other Baseline Characteristics

### 5.4.1. Demographic data

Summary statistics for quantitative data will be calculated for age, weight (both at Visit 2 and Visit 4 before each injection), height and BMI. Frequency and percentages will be calculated for sex, contraceptive status, race, ethnic origin and geographic regions.

Demographics will be tabulated by series and overall using FAS1, FAS2 and by contrast agent group using Safety set. Same analyses will be repeated by body regions using FAS1 and FAS2 only.

Listing of demographics will be presented in CSR Appendix 16.2.4.

### 5.4.2. Trial disease

Trial disease diagnosis will be coded in System Organ Classes (SOC) and preferred terms (PT) using the Medical Dictionary for Regulatory Activities (MedDRA) latest version available at the date of data base lock. Summary tables (number and % of patients) grouped by SOC and PT will be presented by series and overall using FAS1 and FAS2. Tables will be sorted by descending frequency of SOC and, within each SOC, by descending frequency of PT.

CONFIDENTIAL	STATISTICAL ANALYSIS PLAN PHASE III TRIAL GDX-44-011 VERSION NO. 2.0	████████ Page 26 / 57
--------------	--	--------------------------

Time between imaging procedure documenting the trial disease and first injection of trial contrast agent will be calculated in months as follow: (first study contrast agent administration date - procedure date in days) / 30.4375.

For imaging procedure, in addition of the two existing pre-specified classes (MRI and CT) 3 classes (mammogram, Ultrasound, PET-CT) will be created. As they are not pre-specified, they will be classified by scanning the specify text when other is ticked according to the following algorithm:

If the upcased string of characters contains "ULTRASOUND" or "ULTRASONOGRAPHY" then the procedure will be classified as Ultrasound.

If the upcased string of characters contains "MAMMOGRAM" or "MAMMOGRAPHY" then the procedure will be classified as Mammogram.

If the upcased string of characters contains "PET-CT" or "PET/CT" or "PET CT" then the procedure will be classified as PET-CT.

Time and imaging procedure will be tabulated by series and overall using FAS1 and FAS2.

Listing of trial disease diagnosis and imaging procedure will be presented in CSR Appendix 16.2.4

